8. RESEARCH QUESTION AND OBJECTIVES

Primary Objective 1: To describe the proportion of Pfizer-BioNTech bivalent mRNA COVID-19/influenza vaccines that are concomitantly administered, and the characteristics of patients who receive concomitant administration.

Primary Objective 2: To estimate vaccine effectiveness (VE) of concomitant administration of a single dose of the mRNA Pfizer-BioNTech bivalent COVID-19 vaccine and a licensed flu vaccine versus either vaccine alone against all-cause hospitalization or acute respiratory illness requiring hospitalization, emergency department/urgent care or outpatient encounters.

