9.3.2. Outcomes

All outcomes will be assessed starting on Day 15. All hospitalization related outcomes in the table below will be ascertained using acute facility stays only. Inpatient stays classified as skilled nursing facility or rehabilitation will not be used. COVID-19 and flu hospitalizations will be assessed in any position and in the primary position to mitigate possibility of hospitalization with the disease versus for the disease.

COVID-19 related endpoints will be identified using the following ICD-10-CM diagnosis code: U07.1.

Influenza will be identified using the following ICD-10-CM diagnosis codes: J09.X, J10.X, J11.X.

We will evaluate three negative control outcomes. These outcomes are unrelated to vaccination and likely share similar confounding patterns for health-seeking behaviors. These negative controls have been used in other studies of comparative VE of influenza vaccines or COVID-19 VE.¹³⁻¹⁵ Urinary tract infection and accidental injury are outcomes that could differentiate patients who seek medical care versus those who do not, and is likely a better choice of outcome for younger adults. Hospitalization in the first 14 days (ie, among recently vaccinated) uses time as a negative control, in that the vaccine likely could not biologically prevent health events until adequate levels of immunity has been achieved.

Table 2. Outcome Variables

Variable	Role	Operational definition
All-cause hospitalization	Outcome	An inpatient (acute facility) claim that meets the following criteria: 
1. Occurs >14 days after the patient's first mRNA bivalent COVID-19 or influenza vaccine dose during the study period.2. Place of service = 21.3. Non-null confinement ID.4. tos_cd = 'FAC_IP.ACUTE'.
Composite COVID-19 related hospitalization/ED/UC (any position)	Outcome	An inpatient (acute facility) claim that meets the following criteria: 
1. Occurs >14 days after the patient's first mRNA bivalent COVID-19 or influenza vaccine dose during the study period.2. Place of service = 21.

PFIZER CONFIDENTIAL

Table 2. Outcome Variables

Variable	Role	Operational definition

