9.3.3. Censoring

The censoring date will be the minimum date in follow-up (starting >14 days after vaccination) of the following variables.

Table 3. Censoring Variables

Variable	Role	Operational definition
Outcome under study	Censoring	See outcome table above. Table 2 .
Disenrollment	Censoring	Date a patient disenrolls from the insurance plan, as indicated in the enrollment file.
End of data	Censoring	14 February 2023
Receipt of second vaccine of the same type	Censoring	Any kind of mRNA bivalent COVID-19 vaccine is considered as a censoring vaccine. See exposure table for vaccination definitions.
Receipt of the other vaccine type	Censoring	Any kind of mRNA bivalent COVID-19 vaccine is considered as a censoring vaccine. See exposure table for vaccination definitions.
Death	Censoring	Death date is assigned the midpoint of the month in which death is reported in the database.
Nirmatrelvir/ritonavir (sensitivity analysis for COVID-19 endpoints)	Censoring	First dispensing for Nirmatrelvir/ritonavir during follow-up using NDC codes.
Influenza treatment (sensitivity analysis for treatment endpoints)	Censoring	First dispensing of any influenza treatments (see outcome table above for definitions) during follow-up using NDC codes.

PFIZER CONFIDENTIAL

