Functional status/mobility	Patient Characteristics	A procedure code indicating decreased functional status or mobility in the 365 days prior to index. Model specification: dichotomous (yes/no)
Wellness visit	Patient Characteristics	A CPT or diagnosis code for wellness visit in the 365 days prior to index. Model specification: dichotomous (yes/no)
Immunocompromised status	Patient Characteristics	Assess this group as the following category (Yes/No): ≥ 1 IC condition. Any code within the 1 year baseline for the following conditions: 
 • Hematologic malignancy • HIV/AIDS • Solid organ transplant • Bone marrow transplant • Primary immunodeficiencies • Immunosuppressive medications (eg, chemotherapy, oral corticosteroids ≥ 20mg of prednisone or equivalent for ≥ 14 days). Model specification: dichotomous (yes/no)
Conditions that place or may place patients at risk of Severe COVID-19	Patient Characteristics	Assess this group as the following category (Yes/No): ≥ 1 high risk condition. Baseline comorbid conditions that place or may place

PFIZER CONFIDENTIAL

Table 4. Covariates

Variable	Role	Operational definition
		
patients at risk of Severe COVID-19 will be assessed in the 12 months prior to index date. Conditions will be assessed by having at least 1 ICD-10-CM code in any position in any setting. The conditions include:
 
• Cancer history• Chronic kidney disease (CKD) at any stage• Chronic liver disease• Chronic lung diseases• Dementia or other neurological conditions• Diabetes (type 1 or type 2)• Disabilities; including Down Syndrome• Heart conditions (heart failure; coronary artery disease; or cardiomyopathies)• HIV infection• Hypertension• Immunocompromised state (primary caused by genetic defects; secondary/acquired from prolonged use of corticosteroids or other immune weakening medicines)• Mental health conditions• Overweight and obesity• Physically inactive• Sickle cell disease (SCD) or thalassemia• Smoking; current or former• Solid organ or blood stem cell transplant (includes bone marrow transplants)• Stroke or cerebrovascular disease• Substance use disorders (alcohol; opioid; or cocaine)

PFIZER CONFIDENTIAL

Table 4. Covariates

Variable	Role	Operational definition
		
use disorder)
 
 • Tuberculosis • Pregnancy or recent pregnancy (for at least 42 days following end of pregnancy). 
Model specification: dichotomous (yes/no)

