Each outcome will be assessed separately. Experiencing one disease specific outcome is not a censoring criteria for the other disease (ie, having a COVID-19 outpatient diagnosis is not a censoring event for the influenza endpoints). Weighted cumulative incidence curves will be used to describe the occurrence of each outcome separately over the entire follow-up period. Given the relatively short follow-up time, we expect small numbers of deaths. Therefore, regular Cox proportional hazards models will be used to estimate HRs and 95% CI for each outcome separately. If we find that death is more common than anticipated, we will consider using Fine and Gray's proportional subdistribution hazards models to account for the competing risk of death. Models for the following vaccine group/outcome combinations will be assessed:

- Same day/COVID-19 only:
 - All-cause hospitalization, composite COVID-19 hospitalization/ED/UC (any position), COVID-19 hospitalization (any position, primary position), COVID-19 ED/UC, COVID-19 outpatient
- Same day/Flu only:
 - All-cause hospitalization, composite flu-hospitalization/ED/UC (any position), flu-hospitalization (any position, primary position), flu ED/UC, flu outpatient.

CCI

Sensitivity Analysis

For disease specific endpoints, we will conduct a sensitivity analysis whereby an additional censoring criteria will be applied. For COVID-19 specific endpoints, we will censor for Paxlovid dispensing. For influenza specific endpoints, we will censor for any of the following influenza treatment dispensing (Oseltamivir phosphate, Zanamivir, Peramivir, Baloxavir marboxil).

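### At ages 18–64, all-cause hospitalization appears to count deliveries, while pregnancy enters the propensity score only inside a 21-condition yes/no flag and so can stay unbalanced and unseen

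*Combined protocol and SAP*

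**What the plan says.** Primary Objective 2 (section 8) estimates effectiveness of same-day vaccination versus either vaccine alone "against all-cause hospitalization or acute respiratory illness requiring hospitalization, emergency department/urgent care or outpatient encounters". Section 9.7 models all-cause hospitalization in both comparisons; the list for same day versus COVID-19 alone reads "All-cause hospitalization, composite COVID-19 hospitalization/ED/UC (any position), COVID-19 hospitalization (any position, primary position), COVID-19 ED/UC, COVID-19 outpatient". All analyses are run separately at 18–64 and 65+.

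Section 9.3.2 says "All hospitalization related outcomes in the table below will be ascertained using acute facility stays only" and "All outcomes will be assessed starting on Day 15". In Table 2, all-cause hospitalization needs place of service 21, a confinement ID and "tos_cd = 'FAC_IP.ACUTE", with no diagnosis restriction. The only stays named as removed are these: "Inpatient stays classified as skilled nursing facility or rehabilitation will not be used". Pregnancy is not among the exclusion criteria in 9.2.2.

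In Table 4 (9.3.4) pregnancy appears once, as "Pregnancy or recent pregnancy (for at least 42 days following end of pregnancy". It is the last of 21 conditions that together form one dichotomous variable for risk of severe COVID-19, assessed over the 12 months before index. Hypertension, overweight, smoking and mental health conditions are in the same variable. Under 9.7 the propensity score takes the Table 4 variables that have a model specification. Balance is checked by standardized mean differences, and variables still imbalanced after weighting are added to the model.

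**The concern.** Unless the data vendor files maternity stays under another type of service, a delivery after Day 14 is an outcome event. Pregnancy at index is then a strong predictor of the outcome, for reasons unrelated to either vaccine. The plan gives a pregnant woman and a smoker the same covariate value. It also gives the same value to a woman due to deliver during follow-up and one whose pregnancy has already ended.

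If pregnant women choose same-day vaccination more or less often than others of similar age and sex, the 18–64 hazard ratio for an outcome named in the primary objective would partly reflect obstetric case mix. The rule that adds imbalanced variables to the model cannot act on a variable that has no row of its own.

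**Working it through.** **1. Is there a figure in the plan to reproduce?** Not for this outcome: section 9.5 gives no event rate, margin or power for all-cause hospitalization. The event formula behind 9.5 can be checked on the 65+ endpoints: (1.960 + 0.842)² / [a(1−a)(ln 1.15)²]. With a = 0.63 it gives 1,724 events and with a = 0.23 it gives 2,269, both as stated. The matching standard error is used in step 6.

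**2. Time at risk.** From Day 15 to the end of data ("14 February 2023") is about 153 days for an index date of 31 August, 108 for 15 October and 77 for 15 November. Assuming a pregnancy of roughly 280 days and women spread evenly over gestation, 77/280 = 28% and 108/280 = 39% would deliver in the window. Earlier censoring, for example on receipt of the other vaccine, lowers this. The value used in step 3 is 25–35%.

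**3. Apparent ratio with no vaccine effect.** R = (b + p₁d)/(b + p₂d), where b is background (non-delivery) admission risk, d the share of pregnant women delivering in follow-up, and p₁ and p₂ pregnancy prevalence in the two groups after weighting. None of these is in the documents; all are assumed.

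| b | d | p₁ | p₂ | R | Groups reversed |
|---|---|---|---|---|---|
| 2% | 25% | 1.0% | 1.25% | 0.0225/0.023125 = 0.973 | 1.028 |
| 2% | 25% | 1.0% | 1.5% | 0.0225/0.02375 = 0.947 | 1.056 |
| 1% | 35% | 1.0% | 1.25% | 0.0135/0.014375 = 0.939 | 1.065 |
| 1% | 35% | 1.0% | 1.5% | 0.0135/0.01525 = 0.885 | 1.130 |

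**4. Smaller gaps, on the hazard-ratio scale.** HR = ln(1−r_A)/ln(1−r_B), with r = b(1−q) + [d + (1−d)b]q and q the pregnancy prevalence. Take b = 1.5%, d = 30% and q = 1.0% in the reference group. A gap of 0.1, 0.2 or 0.5 percentage points gives 1.017, 1.033 or 1.083. Over b 1–3%, d 20–40% and q 0.5–2%, the ranges are 1.006–1.033, 1.012–1.067 and 1.029–1.166. In the b = 1.5% case the standardized differences for pregnancy are only 0.010, 0.019 and 0.045.

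**5. Does the planned weighting remove the gap?** This was simulated in 1.5 million people with no vaccine effect. Assumed inputs were 4% of women under 45 pregnant, 30% of them delivering, and background risk 2% with the flag and 1% without. The logistic score used sex, linear age, the flag, outpatient visits, labs and office setting.

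| Odds ratio, pregnancy and same-day vaccination | Gap before weighting (points) | Gap after weighting (points) | Apparent HR | HR with pregnancy in the score |
|---|---|---|---|---|
| 0.6 | 0.77 | 0.62 | 0.904 | 1.000 |
| 0.8 | 0.41 | 0.29 | 0.954 | 1.000 |
| 1.3 | 0.24 | 0.32 | 1.054 | 1.000 |

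The flag itself balanced to within 0.0001 each time.

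**6. Would such shifts stand out from noise?** SE(ln HR) = 1/√[events × a(1−a)], at an assumed overall admission risk of 1.5% and the Table 5 counts.
- Versus COVID-19 alone: (244,864 + 144,695) × 0.015 = 5,843 events, SE 0.027, 95% CI factor 1.054.
- Versus flu alone: (244,864 + 772,418) × 0.015 = 15,259 events, SE 0.019, factor 1.038. A spurious HR of 1.05 would be called different from 1 about 73% of the time.

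**The case against.** The strongest objection is that the premise depends on a vendor field the documents do not define. If maternity stays carry a type-of-service value other than the acute one, deliveries are already outside the outcome and most of the point falls. That stands as a condition to be checked. Redacted rows of Table 2 and redacted text in 9.7 cannot be checked either.

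Second, every input to the size is assumed, and nothing in the documents says that pregnancy is associated with same-day vaccination in either direction. This also stands. The simulation imposed the association, so it shows the mechanism and not that bias is present.

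Third, the plan has partial safeguards. Age, sex, visit counts, labs, wellness visits, index month and vaccination setting are in the score, and hospitalization on Days 1–14 is a negative control that near-term deliveries could disturb. The proxies that were simulated did not close the gap, although not all of the plan's proxies were included. The negative control may hint at a problem, but it does not correct one, and no rule says what follows if it is positive.

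Some stronger readings are not supported:
- A reader might infer that a woman pregnant at index will very probably be admitted. Follow-up is too short for most index dates.
- A reader might set these shifts against the 1.15 margin. Section 9.5 uses that margin only for COVID-19 and influenza endpoints, and none is stated for all-cause hospitalization.
- A reader might object that deliveries dilute the ratio toward 1. That is true of any admission the vaccines do not prevent, and it comes with choosing an all-cause outcome.

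**Conclusion.** The concern holds in a conditional form. The structure is plain from the text: no visible delivery exclusion, no pregnancy exclusion, and pregnancy present in the score only through a broad flag. The balance check and the residual-imbalance rule therefore cannot reach it.

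The size is not established. Under the assumptions in step 3 the apparent ratio with no vaccine effect is about 0.89–0.97, or 1.03–1.13 with the imbalance reversed. At a residual gap of 0.1 percentage points the shift is only about 1–3%. The direction is unknown, and a reader should not infer that the planned estimate is biased in any particular direction, or that bias has been shown. The result also requires that delivery stays carry the acute-facility code.

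The scope is one outcome in one age group. The 65+ results, and the outcomes that need a COVID-19 or influenza code, are not affected.

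**What to change.** First confirm with the data vendor how maternity confinements are classed, and state the answer in Table 2.

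In Table 4, add pregnant at index (yes/no; model specification: dichotomous) as its own covariate and its own standardized-difference row in the two 18–64 propensity models. Current pregnancy must be separated from ended pregnancy within the existing pregnancy codes, because the listed item covers both over 12 months. The term in the score matters more than the balance row: gaps large enough to matter give standardized differences below 0.05 in step 4, and the plan states no threshold.

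In Table 2 and section 9.7, report 18–64 all-cause hospitalization with delivery stays removed as a sensitivity analysis alongside the planned definition.

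The cost is a small algorithm for current pregnancy, a delivery code list, one extra run, and slightly fewer events in that run. A yes/no term does not capture gestational age, which is one reason to have the delivery-excluded analysis as well.

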Influenza-related hospitalization (any position)	Outcome	
An inpatient (acute facility) claim that meets the following criteria:
 
 1. Occurs >14 days after the patient's first mRNA bivalent COVID-19 or influenza vaccine dose during the study period. 2. Place of service = 21.

PFIZER CONFIDENTIAL

Table 2. Outcome Variables

Variable	Role	Operational definition
		
3. Non-null confinement ID.
 
4. tos_cd = 'FAC_IP.ACUTE'.
 
5. Influenza diagnosis code (ICD-10-CM: J09.X, J10.X, J11.X) in any position.

CCI		                                              
COVID-19 related ED/Urgent care visit (any position)	Outcome	
An ED/urgent care claim that meets the following criteria:
 
 1. Occurs >14 days after the patient's first mRNA bivalent COVID-19 or influenza vaccine dose during the study period. 2. Place of service = 23 or 20. 3. Confinement id = null. 4. COVID-19 diagnosis code (ICD-10-CM: U07.1) in any position.
Influenza-related ED/Urgent care visit (any position)	Outcome	
An ED/urgent care claim that meets the following criteria:
 
 1. Occurs >14 days after the patient's first mRNA bivalent COVID-19 or influenza vaccine dose during the study period. 2. Place of service = 23 or 20. 3. Confinement id = null.

PFIZER CONFIDENTIAL

Table 2. Outcome Variables

Variable	Role	Operational definition
		4. Influenza diagnosis code (ICD-10-CM: J09.X, J10.X, J11.X) in any position.
COVID-19related outpatient visit (any position)	Outcome	
An outpatient claim that meets the following criteria:
 
 1. Occurs >14 days after the patient's first mRNA bivalent COVID-19 or influenza vaccine dose during the study period. 2. Confinement id = null. 3. COVID-19 diagnosis code (ICD-10-CM: U07.1) in any position. 4. Does not meet the definition of an ED/UC/hospital visit.
Influenza-related outpatient visit (any position)	Outcome	
An outpatient claim that meets the following criteria:
 
 1. Occurs >14 days after the patient's first mRNA bivalent COVID-19 or influenza vaccine dose during the study period. 2. Confinement id = null. 3. Influenza diagnosis code (ICD-10-CM: J09.X, J10.X, J11.X) in any position. 4. Does not meet the definition of an ED/UC/hospital visit.

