Number of outpatient visits in the 180 days prior	Patient Characteristics	
Count unique days with an outpatient visit in the 180 days prior to index
 
 • Dichotomous, yes/no • Continuous statistics including mean, standard deviation (SD), median (Q1-Q3), minimum, and maximum. 
Model specification: number categories (0, 1, 2, 3+)

Number of hospitalizations in the 180 days prior	Patient Characteristics	
Count of unique days with an acute hospital admission (POS = 21 and tos_cd = 'FAC_IP.ACUTE') in the 180 days prior to index
 
 • Dichotomous, yes/no • Continuous statistics including mean, standard deviation (SD), median (Q1-Q3), minimum, and maximum 
Model specification: number categories (0, 1, 2+)

Number of prior COVID-19 tests in the prior 365 days	Patient Characteristics	
Count of unique days with COVID-19 test (PCR or antigen test) ordered in the 365 days prior to index
 
 • Dichotomous, yes/no • Continuous statistics including mean, standard deviation (SD), median (Q1-Q3), minimum, and maximum 
Model specification: number categories (0, 1, 2+)

Flu test in the prior 365 days	Patient Characteristics	
Influenza test ordered in the 365 days prior to index
 
 • Dichotomous, yes/no 
Model specification: dichotomous (yes/no)

Number of prior telehealth visits in the prior 365 days	Patient Characteristics	
Count of unique days with telehealth visit in the 365 days prior to index
 
 • Dichotomous, yes/no

PFIZER CONFIDENTIAL

Table 4. Covariates		
Variable	Role	Operational definition
		
 Continuous statistics including mean, standard deviation (SD), median (Q1-Q3), minimum, and maximum 
Model specification: number categories (0, 1, 2+)

Number of labs ordered in the prior 365 days	Patient Characteristics	
Count of unique days with any lab ordered in the 365 days prior to index
 
 Dichotomous, yes/no Continuous statistics including mean, standard deviation (SD), median (Q1 -Q3), minimum, and maximum 
Model specification: number categories (0, 1, 2+)

Prior COVID-19 infection	Patient Characteristics	
1 ICD-10-CM code (U07.1) in the 1 year baseline in any setting (>3 months prior to reflect exclusion criteria
 
Model specification: dichotomous (yes/no)

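### Prior ED/urgent-care use is not a separate covariate, so differences in it that the listed covariates do not explain may bias the ED/UC and composite hazard ratios in either direction

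*Combined protocol and SAP*

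**What the plan says.** Section 9.7 builds two propensity scores (same day vs COVID-19 alone, same day vs flu alone) from the section 9.3.4 covariates that carry a model specification. The main health-care-use rows in Table 4 are:

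- "Number of outpatient visits in the 180 days prior", defined as "Count unique days with an outpatient visit in the 180 days prior to index" and modelled as 0, 1, 2, 3+. No place-of-service (POS) rule is given.
- "Number of hospitalizations in the 180 days prior", defined as "Count of unique days with an acute hospital admission (POS = 21 and tos_cd = 'FAC_IP.ACUTE') in the 180 days prior to index" and modelled as 0, 1, 2+.
- Telehealth: "Count of unique days with telehealth visit in the 365 days prior to index".
- Labs: "Count of unique days with any lab ordered in the 365 days prior to index".
- COVID-19 tests, influenza test and wellness visit, each over 365 days.

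No row counts prior ED or urgent-care visits, and Table 4 shows no blacked-out row.

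On the outcome side, section 9.3.2 defines an ED/UC visit as POS 23 or 20 with a null confinement ID. It is an endpoint for each disease and one arm of each composite. The outpatient outcome carries a separate condition, "Does not meet the definition of an ED/UC/hospital visit". The COVID-19 models in section 9.7 include "composite COVID-19 hospitalization/ED/UC (any position), COVID-19 hospitalization (any position, primary position), COVID-19 ED/UC, COVID-19 outpatient"; the influenza list runs parallel.

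**The concern.** The plan measures outcomes in three care settings: hospital, ED/UC and outpatient. It adjusts explicitly for prior use of the first and third. Prior use of a setting is normally a good predictor of later use of it. If same-day recipients differ from single-vaccine recipients in how readily they use the ED or urgent care, and the other covariates do not account for that, the ED/UC and composite HRs can move away from 1 with no vaccine effect.

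The standardized mean differences cannot reveal an imbalance in a variable that is never derived, and the rule adjusting further for residual imbalance cannot act on it. Against a margin of 1.15, a shift of a few percent can change the conclusion. A downward shift makes a false non-inferiority finding more likely; an upward shift can hide true non-inferiority.

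**Working it through.** **1. Reproduce the plan's sizing (section 9.5, age 65+).** Events = (1.960 + 0.842)² / [q(1−q)(ln 1.15)²], where q is the Group 1 share; patients = events / event rate.

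- COVID-19 composite, q = 0.63: 1,724 events (plan 1,724). 1,724 / 0.0056 gives 193,950 + 113,907 patients (plan 193,548 + 113,671).
- Influenza composite, q = 0.23: 2,269 events (plan 2,269). 2,269 / 0.003 gives 173,957 + 582,377 patients (plan 176,179 + 589,817).

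Both agree within 3%, so the sizing is as stated. An added covariate does not change these figures.

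**2. Expected events from Table 5 (age 65+).**

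- COVID-19: (382,806 + 225,842) × 0.56% = 608,648 × 0.0056 = about 3,408 events, q = 0.6289.
- Influenza: (382,806 + 1,351,093) × 0.3% = 1,733,899 × 0.003 = about 5,202 events, q = 0.2208.

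**3. How large might the bias be?** The documents give neither the prevalence of prior ED/UC use by group nor its association with the endpoints, so these inputs are assumptions. For a binary confounder,

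bias factor = [1 + p1(RR − 1)] / [1 + p0(RR − 1)],

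where p1 and p0 are the proportions of prior ED/UC users in Group 1 and the comparator after weighting, and RR is the endpoint rate ratio for prior users. With p0 = 20%:

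| Residual imbalance | RR 1.5 | RR 2 | RR 3 |
|---|---|---|---|
| −5 points | 0.977 | 0.958 | 0.929 |
| −2 points | 0.991 | 0.983 | 0.971 |
| +2 points | 1.009 | 1.017 | 1.029 |
| +5 points | 1.023 | 1.042 | 1.071 |

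The outer range is 0.93 to 1.07. Letting p0 run from 15% to 30% widens it to 0.92 to 1.08. The mildest cells are under 1%.

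**4. What does a shift of that size do?** With E events, the chance that the upper 95% limit falls below 1.15 is

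P = Φ( √[E q(1−q)] × (ln 1.15 − ln apparent HR) − 1.96 ).

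| Age 65+, Table 5 sample | COVID-19 composite | Influenza composite |
|---|---|---|
| True HR 1, no bias | 97.6% | 98.7% |
| True HR 1, biased to 1.03 | 87.5% | 90.9% |
| True HR 1, biased to 1.05 | 72.8% | 77.7% |
| True HR 1.15, no bias (false non-inferiority) | 2.5% | 2.5% |
| True HR 1.15, bias factor 0.97 | 13.5% | 14.7% |
| True HR 1.15, bias factor 0.95 | 30.4% | 33.5% |

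At the plan's minimum event counts (1,724 and 2,269), power is 80% without bias, 60% at an apparent HR of 1.03 and 45% at 1.05. False non-inferiority is 8.9% with a factor of 0.97 and 17.6% with 0.95. These figures ignore the information lost through weighting.

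**The case against.** Four points can fairly be made for the plan.

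- **Correlated covariates are already in the scores.** Outpatient visits, admissions, telehealth, labs, tests, wellness visit, comorbidity index, high-risk conditions and vaccine administration setting will absorb part of any difference. Prior COVID-19 and influenza infection are coded in any setting, so episodes seen in the ED count there. A reader might infer that differences in habitual ED/UC use pass straight into the HRs. The documents do not support that: only the unexplained part is left.
- **The outpatient count may include ED/UC days.** A reader might infer from the outpatient outcome, which excludes them, that the baseline count does too. The covariate row does not say so. This is an ambiguity, not an established exclusion. Even if the days are counted, someone with three office visits and someone with three ED visits share the 3+ category, so ED/UC use is still not balanced separately.
- **Negative controls are planned.** Section 9.3.2 uses urinary tract infection and accidental injury in any setting, partly to detect differences in care-seeking, plus hospitalization in the first 14 days. They may raise a flag. They do not adjust, none is specific to ED/UC, and the visible text gives no rule for acting on a signal.
- **The endpoints are narrower than general ED/UC use, and the margin appears only in section 9.5.** An ED/UC event needs a COVID-19 or influenza code, so general ED/UC use is one step removed. Section 9.7 plans HRs and confidence intervals without a visible non-inferiority decision rule, although section 9.5 refers to non-inferiority analyses. This tempers the point but does not remove it: a biased HR is biased whether or not it is tested against a margin.

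**Conclusion.** The point holds as a gap in the adjustment set. ED/UC use is an outcome setting with no separate baseline counterpart, and the one covariate that might contain it is undefined on this. The bias is possible, not demonstrated. Its size and direction cannot be found from the documents; the range of 0.93 to 1.07 rests on the assumed prevalence, residual imbalance and rate ratios above.

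A reader might also infer that the omission favours non-inferiority. Nothing in the documents indicates which group uses the ED or urgent care more, so an upward shift is as plausible as a downward one. The consequence falls mainly on age 65+. For ages 18-64 the plan itself says neither composite reaches the required sample size. The improvement is worth making because a shift of 3% to 5% matters at this margin and the remedy costs little.

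**What to change.** Add a row to Table 4: number of ED/urgent-care visits in the 365 days before index, counted as unique days with POS 23 or 20 and a null confinement ID; model specification categorical (0, 1, 2, 3+). Include it in both propensity scores and in the standardized-mean-difference tables for both comparisons. State in the outpatient-visit row that these days are excluded from that count.

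The cost is one more derived variable, using the place-of-service rule already written for the outcomes and the existing one-year lookback. It needs no new data and loses no patients. Weight variability may rise slightly.
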